6.4. Handling of Missing, Unused, and Spurious Data and Dropouts

The mortality rate in this patient population is anticipated to be low. The total assumed attrition rate through one year is 10%. Two general strategies will be used to mitigate the impact of missing data in this study. First, most objectives will be analyzed using Kaplan-Meier survival analysis methods, which allow data from subjects with less than 12-months of follow-up to still be utilized up until their last date of contact. Second, to test the sensitivity of the primary efficacy and safety analyses to the range of values possible, but unobserved in subjects exiting prior to 12 months, tipping point analyses will be performed on the full analysis set.

The tipping point analysis methods will be as follows. For subjects in the mITT dataset with less than 12-months of follow-up, each subject will be set to treatment failure (failure date set to date of study exit + 1 day). The 12-month Kaplan-Meier estimate will be re-calculated with the earliest (closest to index ablation) sequentially added to the Kaplan-Meier analysis, and the results presented in table format. The tipping point will be defined as the number of additional failures in which the 40% OPC is crossed by the lower 95% confidence bound.

Those subjects with less than 12 months of data will be compared with completers in terms of baseline covariates, and results will be displayed in table form. For either primary endpoint, if fewer than 5 subjects have missing data, a worst-case analysis will be done instead of a tipping point analysis.

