13.10. Scheduled Follow-up Visits

After receiving notice of completed study procedure, Medtronic will provide the target dates and windows for each visit to the center. Should a subject miss a visit or the visit fall outside the pre-specified window, a study deviation must be reported and the original follow-up schedule maintained for subsequent visits.

Data analyses include follow-up visits, regardless of whether the visit occurs within the window. Therefore, a late visit is preferred over a missed visit but must be accompanied by a deviation. Follow-up visit windows are listed in Table 8 and are based on days after the index ablation procedure.

Table 8: Follow-up Schedule

Occurrence/ Visit	Window (Calculated days after the ablation procedure)		
	Window Start	Target	Window End
Enrollment/Baseline	-30 days	-15 days	Day 0
Index Cryoablation Procedure	Day 0	Day 0	Day 0
6 week phone call	35 days	39 days	42 days
3 month office	91 days	91 days	121 days
6 month office	165 days	180 days	195 days
12 month office	365 days	365 days	395 days

The following information is required to be collected at the follow-up visits:

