13.19. Subject Withdrawal or Discontinuation

A subject can withdraw from the study or the [REDACTED] sub-study at any time. If the subject wishes to exit from the study (i.e. the subject revokes consent), the center is required to document the reason for exit on an eCRF. In addition, centers shall follow the regulations set forth by their IRB/MEC. It is recommended to follow the subject until all ongoing device and/or procedure-related adverse events are resolved or unresolved with no further actions planned. For countries following ISO, permission may be requested to follow-up with the subject outside of the study due to withdrawal based on problems related to the study device safety or performance. Following exit, subjects will continue to receive standard medical care. All data available through the time of the subject's exit will be used for analysis.

Reasons for study exit include:

- Subject lost to follow-up
- Subject did not meet inclusion/exclusion criteria after consent and did not undergo an ablation procedure
- An Arctic Front Advance catheter was not used during the subject's ablation procedure
- Subject did not provide consent or data use protection authorization
- Subject chooses to withdraw (e.g., consent withdrawal, relocation to another geographic location)
- Investigator deems withdrawal necessary (e.g., medically justified, inclusion/exclusion criteria not met, failure of subject to maintain adequate study compliance)
- The sponsor decides the study will be closed or a particular center will be closed

The following information is required to be collected at study exit:

- Reason for exit must be documented on the eCRF and in the subject's medical record

In the case that the subject is determined to be lost to follow-up, details of a minimum of two attempts and the method of attempt (e.g., one letter and one phone record or two letters) to contact the subject must be recorded.

An unscheduled office visit should be attempted if the subject exits the study outside of a scheduled follow-up visit.

14. Risks and Benefits

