Table 12 summarizes the published literature of 12-month efficacy rates for Cryoballoon PVI ablation. The summary estimates 12-month efficacy to be 59.3%. Due to more stringent endpoint definition, increased monitoring, and the potential for publication bias, this study protocol assumes a 12 month efficacy rate of 54% for the sample size calculation. With 150 enrolled and treated subjects, minus an assumed 10% attrition rate, the expected number of subjects with 12 months of follow-up at the final analysis is 135.

For the US/Canada/Europe/Japan cohort, 165 treated subjects affords 92% power to test the primary endpoint based on the same assumptions. With 165 enrolled and treated subjects, minus an assumed 10% attrition rate, the expected number of subjects with 12 months of follow-up at the final analysis is 148.

Determination of Subjects/Data for Analysis

All enrolled subjects who have the Arctic Front Advance Cardiac CryoAblation Catheter inserted into vasculature will be included.

Sensitivity Analyses

A sensitivity analysis will be conducted to estimate the potential impact of subjects with less than 12 months of follow-up at the final analysis. The mortality rate in this patient population is anticipated to be low. The total assumed attrition rate through one year is 10%. Because the primary endpoint will be tested using survival methods, all treated subjects are included in the primary analysis, and therefore no subjects will have complete missing data. For subjects that exit early, a tipping point analysis will be conducted to estimate the potential impact of subjects with less than 12-months of follow-up. These subjects will be defined as subjects with partial data. The tipping point analysis methods will be as follows. For each subject with less than 12-months of follow-up, each subject will be set to treatment failure (failure date set to date of study exit). The 12-month Kaplan-Meier estimate will be re-calculated with the earliest (closest to index ablation) sequentially added to the Kaplan-Meier analysis, and the results presented in table format. The tipping point will be defined as the number of additional failures in which the 40% OPC is crossed by the lower 95% confidence bound.

Medtronic Confidential

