6.2.2.3. Analysis Methods

The probability of a subject achieving effectiveness success at 12 months (365 days) will be estimated using survival analysis, the Kaplan-Meier method. The standard error will be approximated using Greenwood's formula. A two-sided 95% log-log confidence interval for the probability will be constructed. For every treated subject, day 0 is defined as the day of the index cryoablation procedure. For subjects with treatment failure, the survival date will be set to the date of the treatment failure. For subjects without treatment failure through 12 months, those subjects will be censored at the last study contact date recorded on CRF which may include the last study visit, the exit date, or death date. If a subject without a treatment failure is lost to follow-up, the censoring date will be set to the last known study visit date.

For the component of the endpoint, documented AF/AT/AFL, if this documentation resulted from rhythm monitoring occurring at the 12-month visit within the 12-month visit window, the date of recurrence will be set to 365 days from the study ablation procedure so that these events will be counted as treatment failures in the 12-month Kaplan-Meier analysis. This objective will be analyzed in the mITT dataset: all enrolled subjects who have the Arctic Front Advance Cardiac CryoAblation Catheter inserted into vasculature will be included.

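### The tipping-point analysis dates imputed failures from study exit, so a lost subject whose exit is recorded at or after day 365 is counted event-free or is not tested at all.

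*SAP*

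**What the plan says.** **Primary analysis.** SAP 6.2.2.3 estimates success by Kaplan-Meier at day 365, with Greenwood's standard error and a log-log 95% interval. For lost subjects: "If a subject without a treatment failure is lost to follow-up, the censoring date will be set to the last known study visit date". CIP 17.3.1 has the same rule. One rule moves an event back to day 365, and it covers only AF/AT/AFL documented by monitoring at the 12-month visit within its window.

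**Tipping-point analysis.** SAP 6.4: "each subject will be set to treatment failure (failure date set to date of study exit + 1 day"). CIP 17.3.1: "each subject will be set to treatment failure (failure date set to date of study exit"), without the extra day. Neither caps the date. Subjects are added one at a time, those closest to the index ablation first, and the tipping point is the number of added failures at which the lower bound crosses 40%.

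**Who is imputed.** SAP 6.4 describes the set in two ways. Its purpose is to cover outcomes "unobserved in subjects exiting prior to 12 months". Its rule is "For subjects in the mITT dataset with less than 12-months of follow-up". Neither states whether follow-up ends at the last visit or at exit.

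**Timing of exit.** The 12-month window in CIP Table 8 runs from day 365 to day 395, and CIP 13.10 says "a late visit is preferred over a missed visit but must be accompanied by a deviation". For a lost subject, CIP 13.19 requires "details of a minimum of two attempts and the method of attempt" to be recorded.

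**The concern.** For a lost subject the last visit and the recorded exit can be months apart. The primary analysis uses the first date and the stress test uses the second. A subject last seen at month 6, who misses month 12 and is declared lost after the contact attempts, can have an exit date past day 365. There are then two possibilities:

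- If follow-up ends at the last visit, the subject enters the imputed set but the failure falls after day 365. The subject moves from censored at about day 180 to at risk and event-free through day 365. Imputing a failure raises the estimate.
- If follow-up ends at exit, the subject has 12 months, is not imputed, and stays censored at the last visit.

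Either way the subject is not stress-tested. This is the plan's main check of the efficacy result against dropout, so an understated or missing tipping point would make the result look more robust than it is.

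**Working it through.** **Plan's own figures.** The documents give no numerical result for the tipping-point analysis. The SAP 7.1 power figure reproduces: exact binomial, N = 135, critical value 66, null rate 0.40, alternative 0.54, gives actual alpha 0.0224 and power 0.899. It does not depend on the dating rule.

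**Inputs from the documents.** 150 treated subjects; 10% attrition, so 15 subjects; 40% goal; success read at day 365; log-log 95% bounds.

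**Assumptions.** All 15 are lost, failure-free and last seen on day 180. Early exits are on day 300 and late exits on day 400. Three failures fall on day 0 and the rest are spread over days 91 to 365. Completers are event-free at day 380. With 63 failures the Kaplan-Meier estimate is 54.4%, close to the planned 54%.

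**Formula.** When nobody is censored before day 365, the Kaplan-Meier estimate is S = (150 − failures by day 365)/150 and Greenwood's formula reduces to SE = √(S(1−S)/150). The lower bound is S^exp(1.96 × SE/(S·|ln S|)).

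**63 failures, all 15 lost subjects imputed:**

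- Failure at last visit + 1 day: S = (150 − 63 − 15)/150 = 0.480; SE = 0.0408; SE/(S·|ln S|) = 0.1158; exponent 1.255; lower bound 0.480^1.255 = **39.8%**.
- All 15 exits late, failures dated day 401: S = (150 − 63)/150 = 0.580; SE = 0.0403; SE/(S·|ln S|) = 0.1276; exponent 1.284; lower bound 0.580^1.284 = **49.7%**.
- Primary analysis, 15 censored at day 180: S = 54.4%, lower bound **45.7%**.

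| Late exits among 15 | Lower bound, late exits imputed after day 365 | Lower bound, late exits left out | Dated at last visit + 1 |
|---|---|---|---|
| 0 | 39.8% | 39.8% | 39.8% |
| 5 | 43.1% | 41.6% | 39.8% |
| 10 | 46.4% | 43.5% | 39.8% |
| 15 | 49.7% | 45.7% | 39.8% |

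With 10 or 15 late exits in the second column, the stress test gives a better bound than the primary analysis.

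**Sequential table, earliest exit first:**

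| Failures | First crossing of 40%, dated at last visit + 1 | Late exits (of 15) that hide the crossing |
|---|---|---|
| 60 | none (lowest bound 41.8%) | not applicable |
| 62 | none (lowest bound 40.5%) | not applicable |
| 63 | 15th addition | 1 or more |
| 64 | 13th | 3 or more |
| 65 | 11th | 5 or more |
| 66 | 9th | 7 or more |
| 68 | 6th | 10 or more |
| 70 | 2nd | 14 or more |

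The last column is the same whether late exits are imputed after day 365 or left out. With 66 failures and 5 late exits the crossing is still shown (39.9% at the 9th addition), but if the late exits are imputed the bound is back up to 41.1% in the last row.

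**Boundary, 63 failures, all 15 with the same exit day.** Exit on day 364 gives 39.8% under both documents. Day 365 gives 49.7% under the SAP and 39.8% under the CIP. Day 366 gives 49.7% under both. SAP and CIP therefore disagree on identical data at day 365.

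**The case against.** The strongest reply is that the intended set is early exits. CIP 17.3.1 introduces the analysis as one for subjects who exit early, and the SAP's statement of purpose agrees. On that reading late-exit subjects keep their primary censoring and nothing moves the wrong way, so the third column above applies. This is fair, but it only selects one of the two branches: those subjects are still untested, and the hidden crossings are unchanged.

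Second, the rule mostly hides the less alarming tipping points. A single late exit matters only where the crossing needs all 15 lost subjects to fail. A crossing at the 2nd addition is hidden only if at least 14 of 15 exits are late. This stands.

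Third, the scenario is the maximum affected class. The 10% attrition covers every cause, and subjects censored at exit or death are not affected. The evidence for late exits is indirect: no timing is set for the contact attempts, and the late-visit preference concerns people who are eventually seen. This also stands, and it is why the effect is given as a range.

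Fourth, SAP 6.4 replaces the tipping-point analysis with a worst-case analysis when fewer than 5 subjects have missing data. At the planned attrition of 15 that would not apply, and the section gives no failure date for it either.

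**Conclusion.** The concern holds and should be fixed. For lost subjects with an exit on or after day 365 (SAP), or after day 365 (CIP), the planned check either counts them event-free at 12 months or leaves them out. Under the assumptions above, with 63 failures, the fully imputed lower bound is 39.8% when failures are dated from the last visit. With 5 to 15 late exits it is 43.1% to 49.7% if those subjects are imputed after day 365, and 41.6% to 45.7% if they are left out. Whether a crossing is hidden depends on the number of late exits, which the documents do not give; with 60 or 62 failures there is no crossing to hide. Exits up to day 364, and subjects censored at their exit date, behave as intended. The primary test, sample size and power are unaffected.

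**What to change.** In SAP 6.4, define the imputed set as subjects without treatment failure whose primary-analysis censoring date is before day 365. Date the imputed failure at that censoring date plus one day, so that it never falls after day 365, and order the sequential additions by the same date. The matching sentence in CIP 17.3.1 should say the same. CIP 17.1 allows a change that is not a principal feature to be described and justified in the study report, so a CIP amendment, with the approvals listed in CIP 19.4, need not be raised for this alone.

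Two wording points can go in the same edit. SAP 6.4 names the full analysis set in one paragraph and the mITT dataset in the next; mITT is the set used for the primary analyses. The section also promises the analysis for safety but defines only the 40% crossing, so the crossing of the 13% goal by the upper bound should be stated.

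The cost is one or two sentences and trivial reprogramming. No new data are needed.

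### The tipping point is counted with the earliest exits failed first, so the reported number is the largest that any order can give; the smallest should be shown beside it

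*SAP*

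**What the plan says.** The primary efficacy estimate is set out in SAP 6.2.2.3: "The probability of a subject achieving effectiveness success at 12 months (365 days) will be estimated using survival analysis, the Kaplan-Meier method". The same section adds "The standard error will be approximated using Greenwood's formula" and "A two-sided 95% log-log confidence interval for the probability will be constructed". Under SAP 6.2.2.4 the objective is met if the lower bound exceeds 40%.

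SAP 6.4 deals with subjects who have less than 12 months of follow-up. Each is turned into a failure ("failure date set to date of study exit + 1 day"), the estimate is "re-calculated with the earliest (closest to index ablation) sequentially added to the Kaplan-Meier analysis", and the steps are tabulated. The result is defined as follows: "The tipping point will be defined as the number of additional failures in which the 40% OPC is crossed by the lower 95% confidence bound".

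Protocol 17.3.1, under Sensitivity Analyses, uses the same order ("The 12-month Kaplan-Meier estimate will be re-calculated with the earliest (closest to index ablation) sequentially added to the Kaplan-Meier analysis") and the same definition, with "failure date set to date of study exit" and no added day.

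Neither document gives a reason for starting with the earliest exits, and neither plans a second order. SAP 6.4 also replaces the tipping point with a worst-case analysis when fewer than 5 subjects have missing data, and it compares early exits with completers on baseline covariates.

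**The concern.** The reported tipping point depends on the order in which exits are failed, and the plan fixes one order. In a Kaplan-Meier estimate a failure counts for more when fewer subjects remain at risk. Starting with the earliest exits uses the least damaging conversions first.

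SAP 6.4 says the analysis is meant to cover the range of outcomes that are possible but unobserved. A single count from one end does not show that range. A reader told that seven added failures are needed to lose the goal would take seven as the margin, although four differently placed failures might be enough. The difference matters most when the trial passes narrowly.

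**Working it through.** **Inputs.** From the documents: 150 treated and 10% attrition, so 150 × 0.10 = 15 exits (Protocol 17.3.1); goal 40%, assumed true success 54% (SAP 6.2.2.1 and 7.1); Kaplan-Meier at day 365, Greenwood variance, log-log limits (SAP 6.2.2.3). Exit and failure times are not given and are assumed below.

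**The plan's own figure.** The documents state no tipping-point number. Their efficacy power reproduces: an exact binomial test with N = 135 and critical value 66 has actual alpha 0.0224 and power 0.899, as in SAP 7.1.

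**Direction (algebra).** Let S be the estimate at day 365, V the Greenwood sum, and n(t) the number at risk at the converted exit. Converting one exit gives

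- S → S × (1 − 1/n(t))
- V → V + 1/[n(t)(n(t) − 1)]
- lower bound L = S^exp(1.96√V / (−ln S))

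A converted subject leaves the risk set at essentially the same time either way, so conversions do not alter each other's n(t). L falls when S falls or V rises, provided −ln S > 1.96√V. That holds here: with S = 0.506, −ln S = 0.681 and 1.96√V is about 0.166. Since n(t) never increases, for any number k of conversions the k earliest exits give the highest bound and the k latest give the lowest.

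As a check, all subsets of size 1 to 11 were enumerated in a data set with 12 exits. The ordering held at every size. At size 6 (924 subsets) the bound was 44.17% for the six earliest and 43.09% for the six latest.

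**One step with numbers.** Constructed data: 150 subjects, 15 exits spread evenly over days 15 to 355, 3 acute failures, the other failures spread over days 92 to 364. Take the case S = 0.506, L = 41.94%, which implies V ≈ 0.00715.

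- Earliest exit, n = 150 − 3 = 147: S = 0.506 × 146/147 = 0.5026; V = 0.00715 + 1/(147 × 146) = 0.00720; L ≈ 41.6%.
- Latest exit, n about 70: S = 0.506 × 69/70 = 0.4988; V = 0.00715 + 1/(70 × 69) = 0.00736; L ≈ 41.2%.

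The first conversion costs about 0.3 points of the bound in one order and about 0.7 in the other.

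**Crossing counts in the same layout:**

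| KM estimate | Lower bound | Earliest-first | Latest-first |
|---|---|---|---|
| 54.9% | 46.3% | 15 | 15 |
| 54.2% | 45.5% | 14 | 13 |
| 53.5% | 44.8% | 13 | 10 |
| 52.7% | 44.1% | 12 | 8 |
| 51.3% | 42.7% | 9 | 5 |
| 50.6% | 41.9% | 7 | 4 |
| 49.8% | 41.2% | 5 | 2 |

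Failing on the exit date or one day later gives the same counts, so the difference between Protocol and SAP on that day has no effect here.

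**Typical size (simulation, N = 150, 1,500 trials per setting).** Mean counts, earliest-first against latest-first, among trials that meet the goal and then tip:

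- Exits uniform over follow-up (10%), about 4% acute failures, 25% of failures at the day-365 visit, the rest uniform over days 91 to 364: 7.7 vs 6.4 (true success 50%), 8.4 vs 7.2 (52%), 9.2 vs 8.0 (54%). Largest gap 5.
- A second set of assumed times, 10% exit hazard: 7.4 vs 5.5 (50%) and 8.8 vs 7.0 (54%). Largest gap 6.

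Earliest-first was never the smaller count. In the first setting it was strictly larger in 77% of trials that tipped. A separate 1,000-trial run with the first set of times put the median gap at 1. At 54% true success, 44% of passing trials tipped at all, the two orders differed in 32% of passing trials, and the gap reached 3 or more in 5%. In the second setting at 54%, 784 of 1,364 passing trials never tipped under either order, so 580/1,364 = 43% did.

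**The case against.** The strongest reply is that earliest-first is defensible. The earliest exits have the most unobserved follow-up, so failure is most plausible for them. The latest exits have been seen failure-free for nearly the whole year, so failing them first starts with the least plausible scenario. A tipping-point analysis asks whether the tipping scenario is believable, not only how few failures it needs. This stands as a reason to keep the planned order. It is not stated in either document, and it does not justify showing that order alone.

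A reader might infer that the analysis is biased toward robustness and that latest-first should replace it. The documents do not support that: it would require the minimum count to be the declared target, and no passage says so or sets an acceptable tipping count.

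A reader might also infer that this is the plan's only protection against missing efficacy data. It is not. SAP 6.4 has the worst-case fallback and the comparison with completers, and the sequential table ends with every exit failed, a row that no ordering can change.

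The mechanism is also milder in some settings. With a quarter of failures at the day-365 visit, about 85 to 89 subjects are at risk at day 355. The most extreme pair of exits then differs in effect by a factor near 1.7, and exits within the blanking period have nearly equal risk sets.

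**Conclusion.** The point holds as one of reporting. Under the planned estimator and interval, the earliest-first crossing count is the maximum over all orders, so it should not be read as the fewest failed exits that could lose the 40% goal. That direction follows from the algebra and does not depend on a scenario.

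The size does depend on assumed exit and failure times. With 150 treated and 10% exits, the mean gap is about 1 to 2 failures among trials that pass and then tip, with median 1 and a maximum of about 5 to 6. Evenly spaced constructed cases show gaps of 0 to 4. The gap grows if attrition exceeds the plan: at 54% true success with the second set of times, the means are 12.0 vs 8.9 at 15% exits and 13.9 vs 9.5 at 20%.

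The order does not touch the primary decision, whether a tipping point exists, the all-exits-failed row, or a trial with fewer than 5 exits. It would be wrong to conclude from this that the efficacy claim itself is less secure.

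**What to change.** In SAP 6.4 and Protocol 17.3.1:

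1. Keep the pre-specified earliest-first column.
2. Add a latest-first column, computed in the same way.
3. State that the crossing is the first step at which the lower bound is 40% or less, matching the success rule in SAP 6.2.2.4.
4. Report the tipping point as a range, from the latest-first count (smallest) to the earliest-first count (largest), with the all-exits-failed result beside it.

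A sentence explaining why earliest-first was chosen would also help.

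No new data are needed, and the primary test and sample size do not change. The cost is one extra column and matching text in two documents. The sponsor also accepts a slightly less favourable minimum figure in the report.
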